The signatures below constitutes the approval of this protocol and the attachments and provide the necessary assurances that this trial will be conducted according to all stipulations of the protocol, including all statements regarding confidentiality, and according to local legal and regulatory requirements and applicable U.S. federal regulations, ISO 14155:2020, ICH guidelines, and the Declaration of Helsinki.

Author & Study Responsible Clinician	See Electronic Signature Report	
- coop on one of the original origi	See Breen ome signamire Report	DATE
Clinical Operations		
Manager	See Electronic Signature Report	D.A.TED
		DATE
Biostatistician	See Electronic Signature Report	
		DATE
Data Management	See Electronic Signature Report	
		DATE
Medical Safety		
Officer	See Electronic Signature Report	
		DATE
Approver	See Electronic Signature Report	
		DATE

CHANGE HISTORY

Version	Originator	Description of Change(s) and Section Number(s) Affected	Justification for Change	Date
1.0		Original Protocol	N/A	July 22, 2022

SYNOPSIS

Protocol Title	Clinical Evaluation of Delefilcon A and Verofilcon A Daily		
	Disposable Toric Soft Contact Lenses Over One Week of Wear		
Sponsor	JJVC, [name]		
Clinical Phase	Descriptive study phase: Post-market		
	Design control phase: Post-market, phase 4		
Trial Registration	This study will be registered on ClinicalTrials.gov by the		
	Sponsor.		
Test Article(s)	Approved Products:		
	Test: DAILIES TOTAL1® for Astigmatism Contact Lenses		
	(DT1fA)		
	Control: PRECISION1 TM for Astigmatism Contact Lenses		
	(P1fA)		
Wear and Replacement	Wear Schedule: Daily wear		
Schedules	Replacement Schedule: Daily disposable		
Objectives	Primary Objective:		
	To evaluate the incidence of grade 3 or higher biomicroscopy		
	findings following a 7(±2) day wear period for DAILIES		
	TOTAL1® for Astigmatism Contact Lenses (DT1fA) relative to		
	PRECISION1 TM for Astigmatism Contact Lenses (P1fA) as		
	control.		
	Exploratory Objectives:		
	To evaluate the subjective comfort, vision and handling, visual		
	acuity, and rotational performance over a $7(\pm 2)$ day wear period		
	for DT1fA relative to P1fA as control.		

Study Endpoints	 Primary endpoint: Incidence of grade 3 or higher biomicroscopy findings using the FDA grading scale following a 7(±2) day wear period Observational endpoints (efficacy): Subjective comfort, vision and handling at fitting and following a 7(±2) day wear period using the CLUE questionnaire High-luminance, high-contrast (HLHC) visual acuity in logMAR measured using ETDRS charts at follow-up Lens orientation at 1 minute and 3 minutes following
	 insertion at fitting Mean and standard deviation of settled lens orientation calculated from repeated measures of settled lens orientation at fitting and follow-up visits
	Observational endpoints (safety): • Adverse events
	All endpoints will be summarized using descriptive statistics only; no formal hypothesis testing is planned.
Study Design	This is a bilateral, dispensing, randomized, controlled, double masked, 2×2 cross-over study. Each subject will be randomly assigned to one of two wear sequences (test followed by control or control followed by test). Each wear period will be $7(\pm 2)$ days, with a $7(\pm 2)$ day washout period between wear periods.
	There will be a total of 4 visits: Visit 1: Screening, baseline evaluation and lens fit #1 Visit 2: Follow-up evaluation for first lens Visit 3: Continuance, lens fit #2 Visit 4: Follow-up evaluation for second lens
	See the flow chart at the end of the synopsis table for a schematic of the study visits and procedures (Figure 1).
Sample Size	This study will have an enrollment target of approximately 66 subjects, with a target of at least 60 to complete (assuming a dropout rate of 10%).
Study Duration	Total study duration including the enrollment period is anticipated to be approximately 8 weeks.
Anticipated Study Population	Subjects will be habitual soft contact lens wearers with bilateral astigmatism who are between 18 and 39 years of age (inclusive).

Eligibility Criteria - Inclusion	Potential subjects must satisfy of all the following criteria to be enrolled in the study.
	Inclusion Criteria following Screening
	The subject must:
	1. Read, understand, and sign the STATEMENT OF INFORMED CONSENT and receive a fully executed copy of the form.
	2. Appear able and willing to adhere to the instructions set forth in this clinical protocol.
	3. Be between 18 and 39 (inclusive) years of age at the time of screening.
	 4. By self-report, habitually wear soft contact lenses in both eyes in a daily reusable or daily disposable wear modality (i.e., not extended wear modality). Habitual wear is defined as a minimum of 6 hours of wear per day, for a minimum of 2 days per week during the past month. 5. Possess a wearable pair of spectacles that provide correction for distance vision.
	Inclusion Criteria at Baseline Evaluation
	The subject must:
	6. Have the spherical component of their vertex-corrected distance refraction must be between -0.875 to -4.625 DS (inclusive) in each eye.
	7. Have the magnitude of the cylindrical component of their vertex-corrected distance refraction between 0.625 DC and 1.625 DC in both eyes.
	8. Have the cylinder axis of their distance refraction between 165° and 15° (i.e., 180±15°, inclusive) or between 75° and 105° (i.e., 90±15°, inclusive) in each eye.
	9. Have best corrected monocular distance visual acuity of
Î.	20/20 1 4 1

20/30 or better in each eye.

Eligibility Criteria – Exclusion

Potential subjects who meet any of the following criteria will be excluded from participating in the study:

Exclusion Criteria following Screening

The subject must not:

- 1. Be currently pregnant or lactating.
- 2. Be diabetic.
- 3. Be currently using any ocular medications or have any ocular infection of any type.
- 4. By self-report, have any ocular or systemic disease, allergies, infection, or use of medication that might contraindicate or interfere with contact lens wear, or otherwise compromise study endpoints, including infectious disease (e.g., hepatitis, tuberculosis), contagious immunosuppressive disease (e.g., Human Immunodeficiency Virus [HIV]), autoimmune disease (e.g., rheumatoid arthritis, Sjögren's syndrome), or history of serious mental illness or seizures. See section 9.1 for additional details regarding excluded systemic medications.
- 5. Have habitually worn rigid gas permeable (RGP) lenses, orthokeratology lenses, or hybrid lenses (e.g., SynergEyes, SoftPerm) within the past 6 months.
- 6. Be currently wearing monovision or multifocal contact lenses.
- 7. Be currently wearing lenses in an extended wear modality.
- 8. Have a history of strabismus or amblyopia.
- 9. Be an employee (e.g., Investigator, Coordinator, Technician) or immediate family member of an employee (including partner, child, parent, grandparent, grandchild or sibling of the employee or their spouse) of the clinical site.
- 10. Have participated in a contact lens or lens care product clinical trial within 7 days prior to study enrollment.

[figure not shown]
Exclusion Criteria at Baseline Evaluation

The subject must not:

- 11. Have clinically significant (grade 3 or higher on the FDA grading scale) slit lamp findings (e.g., corneal edema, neovascularization or staining, tarsal abnormalities or bulbar injection) or other corneal or ocular disease or abnormalities that contraindicate contact lens wear or may otherwise compromise study endpoints (including entropion, ectropion, chalazia, recurrent styes, glaucoma, history of recurrent corneal erosions, aphakia, moderate or above corneal distortion, herpetic keratitis).
- 12. Have fluctuations in vision due to clinically significant dry eye or other ocular conditions.

	13. Have had or have planned (within the study period) any ocular or intraocular surgery (e.g., radial keratotomy, PRK, LASIK, iridotomy, retinal laser photocoagulation, etc.).
Disallowed	Subjects will not be eligible to enroll if they are taking any
Medications/Interventions	ocular medications, or any systemic medications that would
	normally contraindicate contact lens wear or may otherwise
	compromise study endpoints. See section 9.1 for details
	regarding disallowed systemic medications.
Measurements and	The key procedures associated with the observational endpoints
Procedures	for this study will be:
	- Grading of ocular physiology by slit lamp biomicroscopy
	using the FDA grading scale
	- Completion of the CLUE questionnaire at fitting and follow-
	up
	- Measurement of HLHC VA using ETDRS charts at follow-
	up
	- Measurement of toric lens orientation using a slit lamp
	biomicroscope
Microbiology or Other	Not applicable for this study.
Laboratory Testing	
Study Termination	The occurrence of an Unanticipated Adverse Device Effect
	(UADE) or Serious Adverse Event (SAE) for which a causal
	relationship to a test article cannot be ruled out, will result in
	stopping further dispensing investigational product. In the
	event of a UADE or SAE, the Sponsor Medical Monitor may
	unmask the treatment regimen of subject(s) and may discuss
	this with the Principal Investigator before any further subjects
A = 0:110 = 0 Compa1: 0 0 /	are enrolled.
Ancillary Supplies/	Lens cases, fluorescein strips and preservative-free rewetting
Study-Specific Materials Principal Investigator(s)	drops / artificial tears will be supplied for use as needed.
and Study	A full list of Principal Investigators, clinical sites, and institutions is kept separately from the Study Protocol and is
1	included in the study Trial Master File.
Institution(s)/Site(s)	meraded in the study That waster file.

Figure 1: Study Flowchart

COMMONLY USED ABBREVIATIONS, ACRONYMS AND DEFINITIONS OF TERMS

ADE Adverse Device Effect

ADHD Attention Deficit Hyperactivity Disorder
AE Adverse Event/Adverse Experience
BSCVA Best Spectacle Corrected Visual Acuity

CFR Code of Federal Regulations
CLUE Contact Lens User Experience
COM Clinical Operations Manager
COVID-19 Coronavirus Disease 2019
CRA Clinical Research Associate

CRF Case Report Form

CRO Contract Research Organization

D Diopter

DMC Data Monitoring Committee eCRF Electronic Case Report Form EDC Electronic Data Capture

ETDRS Early Treatment Diabetic Retinopathy Study FDA Food and Drug Administration

GCP Good Clinical Practice

HIPAA Health Insurance Portability and Accountability Act

HIV Human Immunodeficiency Virus

IB Investigator's Brochure

ICH The International Council for Harmonization

IDE Investigational Device Exemption
IEC Independent Ethics Committee
IRB Institutional Review Board

ISO International Organization for Standardization

ITT Intent-to-Treat

JJVC Johnson & Johnson Vision Care, Inc.
LASIK Laser-Assisted in Situ Keratomileusis
LogMAR Logarithm of Minimal Angle of Resolution

OD Right Eye
OS Left Eye
OU Both Eyes

PIG Patient Instruction Guide
PQC Product Quality Complaint
PRK Photorefractive Keratectomy
PRO Patient Reported Outcome

QA Quality Assurance

SAE Serious Adverse Event/Serious Adverse Experience

SAP Statistical Analysis Plan SAS Statistical Analysis System

SD Standard Deviation

UADE Unanticipated Adverse Device Effect

USADE Unanticipated Serious Adverse Device Effect

VA Visual Acuity

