3.2. Inclusion Criteria

Potential subjects must satisfy all the following criteria to be enrolled in the study:

Inclusion Criteria following Screening The subject must:

- 1. Read, understand, and sign the STATEMENT OF INFORMED CONSENT and receive a fully executed copy of the form.
- 2. Appear able and willing to adhere to the instructions set forth in this clinical protocol.
- 3. Be between 18 and 39 (inclusive) years of age at the time of screening.
- 4. By self-report, habitually wear soft contact lenses in both eyes in a daily reusable or daily disposable wear modality (i.e., not extended wear modality). Habitual wear is defined as a minimum of 6 hours of wear per day, for a minimum of 2 days per week during the past month.
- 5. Possess a wearable pair of spectacles that provide correction for distance vision.

Inclusion Criteria at Baseline Evaluation

The subject must:

- 6. Have the spherical component of their vertex-corrected distance refraction must be between -0.875 to -4.625 DS (inclusive) in each eye.
- 7. Have the magnitude of the cylindrical component of their vertex-corrected distance refraction between 0.625 DC and 1.625 DC in both eyes.
- 8. Have the cylinder axis of their distance refraction between 165° and 15° (i.e., 180±15°, inclusive) or between 75° and 105° (i.e., 90±15°, inclusive) in each eye.
- 9. Have best corrected monocular distance visual acuity of 20/30 or better in each eye.

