4.3. Enrollment Target and Study Duration

This study will have an enrollment target of approximately 66 subjects, with a target of at least 60 to complete. The study will be conducted at up to 5 clinical sites, where the enrollment target for each site will be approximately 14 subjects. A subject will be considered enrolled upon signing of the informed consent form.

There will be 4 visits in total per subject. The total study duration including the enrollment period is expected to be approximately 8 weeks. Subjects who are discontinued prior to the final evaluation may be replaced at the discretion of the study sponsor. The investigation will end at the time that the study data is hard locked.

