6. STUDY INTERVENTION

6.1. Identity of Test Articles

The following contact lenses will be used in this study:

Table 1: Test Articles

	Test	Control	
Test Article Form	Soft con	Soft contact lens	
Brand and Product Name	DAILIES TOTAL1® for	PRECISION1® for Astigmatism	
	Astigmatism	PRECISION1 - 101 Astigitiatism	
Manufacturer	Alcon Labo	ratories, Inc.	
Packaging Form	Blister packaging in s	terile packing solution	
Packaging Solution		solution with wetting agents	
Lens Material	delefilcon A	verofilcon A	
Sphere Powers (DS)	-1.00 to -4.50) in 0.25 steps	
Cylinder Powers (DC)	-0.75,	, -1.25	
Cylinder Axes (°)	10, 80, 90, 1	00, 170, 180	
Nominal Water Content	33%	51%	
(%)	3370	3170	
Nominal Base Curve (mm)	8.6	8.5	
Lens Diameter (mm)	14.5		
Fiducial marks	6 o'clock scribe mark		
Dk (intrinsic Dk- Coulometric method, ×10 ⁻¹¹ [cm ² /sec] [ml O ₂ /ml × mm Hg] at 35°C)	140	90	
Modality in Current Study	Study Daily wear		
Replacement Frequency in Current Study	Lighty disposable		

In total, both test and control lenses will be available in 180 unique lens powers (15 sphere powers \times 2 cylinder powers \times 6 axes).

The total number of test lenses to be used in this study (not including lenses that are replaced due to droppage, loss or damage) is expected to be approximately 924 lenses (target enrollment of 66 subjects × 2 eyes per subject × 7 day wear period). Test and control lenses will be worn in a 1:1 ratio, thus the number of control lenses to be used is expected to be approximately the same (924 lenses).

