7.2. Detailed Study Procedures

VISIT 1

Subjects must wear their habitual contact lenses to this visit.

	Visit 1: Screening			
Step	Procedure	Details		
1.1	Statement of Informed Consent	Each subject must read, understand, and sign the Statement of Informed Consent before being enrolled into the study. The Principal Investigator or his/her designee conducting the informed consent discussion must also sign the consent form.		
		Note: The subject must be provided a signed copy of this document.		
1.2	Demographics	Record the subject's year of birth, age, gender, race and ethnicity.		
1.3	Medical History and Concomitant Medications	Record the subject's medical history and concomitant medications.		
1.4	Habitual Lenses	Record the subject's habitual lens type, parameters, lens care solution, wear modality, and approximate prescription date.		

	Visit 1: Screening			
Step	Procedure	Details		
1.5	Habitual lens wear time.	Record the average and comfortable wear time for the subject's habitual contact lenses.		
1.6	Eligibility after Screening	All responses to Screening Inclusion Criteria questions must be answered "yes" and all responses to Exclusion Criteria must be answered "no" for the subject to be considered eligible. If subject is deemed to be ineligible after screening, proceed to Final Evaluation and complete Subject Disposition. Refraction and		
		Biomicroscopy forms do not need to be completed as part of Final Evaluation.		

		Visit 1: Baseline	
Step	Procedure	Details	
1.7	Subject reported ocular symptoms	Record any subject reported ocular symptoms reported with regard to their habitual contact lenses.	
1.8	Baseline PRO questionnaire	Ask the subject to fill out the baseline questionnaire regarding their experience with their habitual contact lenses.	
1.9	Entrance visual acuity	Record the monocular distance Snellen visual acuity for each eye (OD, OS) to the nearest letter with the subject's habitual contact lens correction. Subjects must continue until at least 50% of the letters on a line are read incorrectly.	
1.10	Remove habitual lenses	The subject's habitual contact lenses will be removed and stored in a lens case, if required.	
1.11	Subjective sphero- cylindrical refraction	Conduct a full spherocylindrical bare eye subjective refraction with binocular balance and record the resultant monocular visual acuity for each eye to the nearest letter. Note: The duo-chrome test should be used for	

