14.2. Sample Size Justification

Approximately 66 subjects will be enrolled in this study to attain a minimum of 60 completed subjects. All endpoints will be summarized using descriptive statistics only; no confirmatory hypotheses will be tested. This is a descriptive study to evaluate the clinical performance of the DT1fA and P1fA lenses. Sample size is not based on the empirical power analysis. The data collected for this study may be used for designing future studies if applicable.

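### Is an enrolment target of about 66 too small to give the 60 completers the plan asks for?

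*Combined protocol and SAP*

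**What the plan says.** The Synopsis gives an "enrollment target of approximately 66 subjects, with a target of at least 60 to complete (assuming a dropout rate of 10" per cent. The dropout rate appears only there, and its base (consented, randomised or dispensed) is not stated. Section 14.2 repeats the aim: "Approximately 66 subjects will be enrolled in this study to attain a minimum of 60 completed subjects". It adds that the number does not come from a power analysis. Section 14.4 says that all planned analyses are descriptive.

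The documents use the word enrolled in more than one sense:

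- Section 4.3: "A subject will be considered enrolled upon signing of the informed consent form".
- Section 3.2: "Potential subjects must satisfy all the following criteria to be enrolled in the study".
- Section 6.1 calculates the lens supply from a "target enrollment of 66 subjects × 2 eyes per subject × 7 day wear period", which treats all 66 as people who wear lenses.

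Section 4.3 plans for at most 5 sites, "where the enrollment target for each site will be approximately 14 subjects". Sections 4.3 and 5.3 let the sponsor replace discontinued subjects. Section 8.2 allows further enrolment after a premature discontinuation, and its withdrawal reasons include failure to be dispensed lenses because of vision, comfort or fit.

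**The concern.** Three things look wrong at first reading.

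First, the stated dropout rate does not quite fit the two targets: a 10% loss from 66 leaves fewer than 60. The figure 66 equals 60 × 1.10, which suggests that the completer target was multiplied by one plus the loss rate instead of divided by one minus it.

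Second, if enrolment is counted at consent, the 66 includes people who never wear a study lens. Section 7.2 places many exits after consent. At screening, for example: "If subject is deemed to be ineligible after screening, proceed to Final Evaluation and complete Subject Disposition". Later exits follow from the refraction limits, the baseline slit lamp examination, the toric and general fit, an over-refraction that calls for an unavailable power, and the dispensing criteria. The fitting steps are repeated at Visit 3. No rate is assumed for any of these losses.

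Third, 5 sites of 14 make 70, not 66.

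With no power calculation, 60 completers is the only commitment the study makes on size. It governs how precisely the incidence of grade 3 or higher findings is estimated for each lens.

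**Working it through.** **Inputs.** Enrolment target 66, completer target 60 and dropout d = 10% (Synopsis); up to 5 sites of about 14 (Section 4.3). The documents give no screening or fitting failure rate, so any value of s below is an assumption.

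**The plan's own figure.**

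- 60 × (1 + 0.10) = 66, the stated number.
- 60 / (1 − 0.10) = 66.67, rounded up to 67.
- Reverse check: 66 × 0.90 = 59.4.
- Largest loss that still leaves 60 of 66: 6/66 = 9.1%.

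The difference is one subject, or 0.6 of an expected completer. No formula is stated, so the origin of 66 is an inference.

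**Chance of at least 60 completers at exactly 10% loss** (binomial, completion probability 0.90, no replacement):

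| Subjects | Expected completers | P(at least 60) |
|---|---|---|
| 66 | 59.4 | 0.51 |
| 67 | 60.3 | 0.65 |
| 70 | 63.0 | 0.91 |

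**If the 66 are consents.** Let a fraction s fail before dispensing and 10% of the rest drop out, again without replacement. Expected completers = 66 × (1 − s) × 0.90; consents needed for 60 = 60 / [(1 − s) × 0.90], rounded up.

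| s (assumed) | Expected completers | Consents needed |
|---|---|---|
| 0% | 59.4 | 67 |
| 5% | 56.4 | 71 |
| 10% | 53.5 | 75 |
| 20% | 47.5 | 84 |
| 30% | 41.6 | 96 |

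**If the 66 are eligible wearers.** Section 6.1 gives 66 × 2 × 7 = 924 lenses of each type, which is a count of people fitted. On that reading screening failures do not use up places, and the gap for later dropout is again 66 against 67.

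**Sites.** 5 × 14 = 70 is the product of a maximum number of sites and an approximate figure per site. It is a ceiling, and it allows 4 more than 66. It does not contradict an approximate total.

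**What precision is at stake.** Take completers as the denominator and, for illustration, suppose no grade 3 finding occurs. The one-sided 95% exact upper limit for the incidence is 1 − 0.05^(1/n):

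- n = 60: 4.9%
- n = 59: 5.0%
- n = 53: 5.5%
- n = 42: 6.9%

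One completer more or fewer moves the limit by about 0.1 percentage point.

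**Which counts enter the analysis.** Section 14.3 defines its populations by lens exposure (Safety), by completion without substantial deviation (Per-Protocol) and by randomisation (ITT). None is defined by enrolment, so the ambiguity of that word does not reach any denominator.

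**The case for a change.** The strongest case for a change leaves the rounding aside and rests on the definition. Under Section 4.3 as written, 66 consents must cover every loss up to Visit 4, with room for only six. With 5% failing before dispensing and 10% of the rest dropping out, the completion probability is 0.95 × 0.90 = 0.855 and the chance of 60 completers from 66 is about 14%. With 10% failing it is 0.81, and the chance is about 2%. Even 70 consents give about 60 expected completers in the first case (70 × 0.855 = 59.9) and 57 in the second (70 × 0.81 = 56.7). Replacement is at the sponsor's discretion, and the plan does not say outright that screening failures are replaced. A sentence of clarification would cost almost nothing.

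Part of this stands. The word is used inconsistently, the base of the 10% is missing, and no failure allowance is written down.

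The inference to a shortfall does not stand. These figures assume that recruitment stops at 66 or 70 consents with nobody added, and the plan says no such thing. The target is approximate, no cap exists, 60 is a stated minimum, and Sections 4.3, 5.3 and 8.2 permit replacement or further enrolment. Fitting and dispensing failures are treated as discontinuations in Sections 7.2 and 8.2, so that permission covers them. Some listed losses are also not automatic: a non-plano over-refraction leads first to a refit, with up to two modifications per eye, and a grade 3 baseline finding allows one repeat evaluation. Nor does a rate described as dropout have to include screening failures.

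**Conclusion.** The concern does not call for a change. The numerical slip is real but amounts to one subject, 66 against 67, in a figure given as approximate. Correcting it would alter no analysis, test or power statement, because the study has no confirmatory test and its size does not rest on power. The mixed use of enrolled is a minor drafting gap. A sponsor working to a minimum of 60 completers, with permission to add subjects, fills it by continuing to recruit.

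This rests on two assumptions: that the sponsor treats 60 as the operative target, as Section 14.2 says, and that it uses the permission to replace or add. If it stopped at 66 consents, fewer would complete (about 53 at an assumed 10% pre-dispensing failure, 42 at 30%) and the descriptive estimates would be less precise. They would still be valid for what they describe, and the report would show the number achieved. The difference between 66 and 5 × 14 needs no reconciling.
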